PCT will be documented by appropriate laboratory measurements carried out in the Porphyria Laboratory at UTMB or another reliable clinical laboratory. This can be done before or after enrollment in an outpatient clinic or at an initial visit to a Clinical Research Center (CRC). Participants are considered to be enrolled after they complete the informed consent process, and will be assigned a Patient Number. Subjects found to be not eligible after enrollment will be recorded as screening failures to be replaced. A recruit to replace approach will be utilized to achieve final recruitment goals. A relapse during follow up can be treated within the study, but will not be part of the primary analysis.

Table 1. Inclusion and exclusion criteria for initial and continued enrollment in the study. Inclusion Criteria:

- 1. Willing to give informed consent
- 2. Willing to return to clinic at time points deemed appropriate by the investigator or work with a local physician to have necessary labs done and samples sent to study site
- 3. Age 18 or greater
- 4. Women of child-bearing potential must be willing to avoid pregnancy and use an accepted and effective contraceptive method during treatment.
- 5. Well-documented PCT:
 - Clinical features- A history of blistering cutaneous photosensitivity and/or skin fragility. Subjects with subclinical PCT who have diagnostic porphyrin elevation but do not have symptoms may also be included.
 - ii.Biochemical and molecular findings a and b are required
 - a. A substantial increase in urinary porphyrins [>450 nmol/24 hours or g of creatinine, or more than 1.5-fold increase (relative to ULN of 300 nmol/24 hours or g of creatinine *or* >300 ug/24 hours or g of creatinine, or more than 1.5-fold increase (relative to ULN of 200 ug/24 hours or g of creatinine)] and/or plasma porphyrins [>2.7 ug/dL, or >3-fold increase (relative to ULN of 0.9 ug/dL), and a fluorescence peak at ~619 nm], with a predominance of uroporphyrin and heptacarboxylateporphyrin in urine or plasma, and normal or only slightly elevated urine ALA and normal PBG.
 - b. Normal or only slightly elevated erythrocyte porphyrins [<200 ug/dL, or less than 1.5-fold increase (relative to ULN of 80 ug/dL)], unless elevated erythrocyte protoporphyrin are due to a non-porphyric condition in the opinion of the investigator. This is to exclude mild cases of CEP and HEP, which may have urine findings similar to PCT.

iii.

Exclusion Criteria:

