Hydroxychloroquine treatment will end after the plasma total porphyrin concentration and other porphyrin abnormalities have been normal for at least one month (i.e. at least one month after all treatment outcomes are achieved). Treatment may be stopped for poor tolerance or other medical reasons, and these reasons will be recorded. For hydroxychloroquine, the desirable length of this treatment and factors that delay response are less well understood, and will be clarified by the results of this study. For this protocol, the duration of hydroxychloroquine treatment will not exceed 24 months.

Either treatment will be discontinued if a participant no longer meets the inclusion criteria or develops one of the exclusion criteria for the assigned treatment. A treatment will also be stopped if an adverse event occurs that is regarded as a reason for stopping the current

treatment or in the judgment of the investigators on clinical grounds is a reason for stopping the current treatment in the best interest of the patient. The reasons for discontinuing treatment will be recorded on the CRFs. If a participant is discontinued from one treatment, they may be switched to the alternate treatment if deemed appropriate by the investigator. Should this happen their information will still be collected according to the schedule described in this protocol and analyzed as part of this study.

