4.O. Adverse experiences. At the time of each visit it will be determined whether any adverse experiences have occurred. The participants will be questioned in a general way and no specific adverse symptoms will be suggested, except in regard to the symptoms to be recorded on the CRFs or symptoms that are of particular importance in the clinical management of an individual patient. Any clinical adverse experiences that have occurred will be recorded on the CRFs, and a judgment made regarding whether or not the adverse experience was related to study treatment.

Any serious adverse experience (SAE), including death, due to any cause and occurring during the course of this investigation, whether or not related to the study treatments or procedures will be reported immediately to the Institutional Review Board (IRB) at the site, the IRB at UTMB, the Clinical Research Center at UTMB and the site, if required, and the US Food and Drug Administration.

A SAE with respect to clinical experience includes any experience that is fatal or life-threatening, is permanently disabling, or either requires or prolongs inpatient hospitalization.

4.P. Patient withdrawal. Every reasonable effort will be made to keep participants in the study. If a patient wishes to leave the study or is removed by the PI, a complete final evaluation will be performed. A narrative description of the reason(s) for withdrawal from the study will be recorded in the source documents.

The following are justifiable reasons for removing a patient from the study:

- 1. Development of a study exclusion criterion, as previously listed
- 2. If continuing the study presents an unacceptable risk or discomfort to the patient.
- 3. Violation of the study protocol.
- 4. The patient is uncooperative or noncompliant in study-related observations or in administration of study medication.
- 5. Consent is withdrawn.
- 6. The study is terminated.

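### The Section 4.H stop for no longer meeting the inclusion criteria contradicts the rule that hydroxychloroquine continues at least one month after all porphyrin outcomes are achieved

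*Combined protocol and SAP*

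**What the plan says.** Section 4.H, End of treatment, contains two rules that bear on when hydroxychloroquine stops.

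- The general clause: "Either treatment will be discontinued if a participant no longer meets the inclusion criteria"; the sentence goes on to add, as a second trigger, developing an exclusion criterion tied to the treatment assigned.
- The specific rule, in the preceding paragraph: "Hydroxychloroquine treatment will end after the plasma total porphyrin concentration and other porphyrin abnormalities have been normal for at least one month". Section 4.C gives the same rule in its treatment definition, with a 24-month maximum.

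The inclusion criteria are in Table 1 (Section 4.E) and are repeated in the synopsis. The Table 1 caption reads "Inclusion and exclusion criteria for initial and continued enrollment in the study". Under criterion 5.ii, "a and b are required". Part a asks for "A substantial increase in urinary porphyrins [>450 nmol/24 hours or g of creatinine, or more than 1.5-fold increase" and/or plasma porphyrins above 2.7 ug/dL with a peak near 619 nm, in either case "with a predominance of uroporphyrin and heptacarboxylateporphyrin in urine or plasma". Nothing in the plan says that 5.ii.a lapses after entry.

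The treatment outcomes (Table 5 and Section 4.K) are normal plasma porphyrins, disappearance of the fluorescence peak, normal urine total, and a urine pattern in which highly carboxylated porphyrins fall below coproporphyrin. Section 4.F runs the Treatment Phase until treatment is complete and every outcome has been reached. Phlebotomy ends on a ferritin target, at which point 4.H expects porphyrins not yet to be normal.

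**The concern.** The entry criterion and the outcomes describe the same measurements from opposite sides. If entry criteria continue to apply during treatment, as the caption says, success on treatment becomes a reason to stop it. For hydroxychloroquine that collides with the requirement to go on past complete remission.

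Three things are at stake.

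- **Arm asymmetry.** The clause bites mainly on hydroxychloroquine. The study compares time to remission and durability between the two treatments, so a rule that shortens one regimen and not the other affects the comparison.
- **Conflict with the redesign.** The interim findings in Section 2 suggested that continuing hydroxychloroquine until the later outcomes normalise may be beneficial. Sections 4.C and 4.H carry that through, and the clause undoes it.
- **Unclear handling afterwards.** For a participant stopped this way and not switched, the plan gives no explicit route. The data-collection sentence in 4.H covers switched participants. The extension of the Treatment Phase past the end of treatment is written for phlebotomy. Section 4.I starts follow-up only once treatment is completed and all outcomes are achieved. Section 4.R has no rule for such a participant.

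**Working it through.** **Inputs.** Entry limits and upper limits of normal (ULN) are from Table 1. The plasma outcome limit of 0.9 mcg/dL is from the recommended practices in Section 4 (4.K prints the same figure per mL; the per-dL unit used elsewhere is taken here). The plan gives no separate figure for a normal urine total, so the Table 1 ULN of 300 nmol is assumed.

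**Step 1. Reproduce the entry limits.**
- Urine: 1.5 × 300 = 450 nmol, and 1.5 × 200 = 300 ug.
- Plasma: 3 × 0.9 = 2.7 ug/dL.

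All agree with Table 1.

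**Step 2. Can all outcomes be reached while 5.ii.a still holds?** Write P for plasma (ug/dL) and U for urine (nmol per 24 h or per g creatinine). The level part of 5.ii.a is (U > 450) or (P > 2.7). The level outcomes together are P < 0.9 and U ≤ 300. Since 0.9 < 2.7 and 300 < 450, no pair (P, U) satisfies both. The result does not depend on taking exactly 300 as normal: any normal limit at or below 450 gives the same answer. The peak and pattern conditions were left out, and they can only make 5.ii.a fail sooner.

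**Step 3. When does 5.ii.a lapse relative to each outcome?**

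| P | U | 5.ii.a levels met | Primary outcome met | Urine total normal |
|---|---|---|---|---|
| 15 | 3000 | yes | no | no |
| 2 | 600 | yes | no | no |
| 2 | 400 | no | no | no |
| 0.8 | 3000 | yes | yes | no |
| 0.8 | 600 | yes | yes | no |
| 0.8 | 400 | no | yes | no |
| 0.8 | 299 | no | yes | yes |

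- Because urine and plasma are joined by and/or, the primary outcome can be reached with 5.ii.a still met (0.8 with 600 or 3000).
- The stop precedes the primary outcome only if U is at or below 450 while P is between 0.9 and 2.7, or if the required pattern or peak is lost first.
- By the time both plasma and urine are normal, 5.ii.a has always lapsed, at the latest at the visit that shows the second normal result.

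**Step 4. Compare the two end dates for hydroxychloroquine.** Let T be the time at which all outcomes are achieved. The inclusion-criteria clause stops treatment at or before T. Sections 4.C and 4.H end it no earlier than T + 1 month. The gap is at least one month for every full responder, unless the 24-month maximum intervenes. Where 5.ii.a lapses before T (for example 0.8 with 400), the gap is larger and the remaining outcomes would be reached off drug.

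**Step 5. Phlebotomy.** Planned treatment ends at ferritin ≤20 ng/mL (or ≤25 ng/mL on the day of the last phlebotomy), which the plan places before porphyrins normalise. Porphyrins could already be below the entry limits without being normal, so the arm is not wholly exempt, but it has no rule requiring treatment past remission and hence no matching contradiction.

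**The case against.** The strongest reply is that criterion 5 is an entry diagnosis. It asks for well-documented PCT, 5.i needs only a history of symptoms, and the Schedule of Events places the documentation of PCT, with ALA, PBG and erythrocyte protoporphyrin, at baseline only. Other Table 1 criteria, such as contraception and pregnancy, do make sense as continuing conditions and may explain the caption. Sections 4.C, 4.F and the preceding paragraph of 4.H all carry treatment through remission, and a specific, repeated rule would usually be read as governing a general clause. This stands as evidence of intent. It does not remove the conflict: nothing marks 5.ii.a as entry-only, the caption says the opposite, and plasma and urine porphyrins are measured throughout treatment, so the lapse is visible to a site.

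A second reply is that the closing words of the clause, about the assigned treatment, point to Tables 3 and 4. Those tables list only contraindications, so the reference to inclusion criteria has nowhere to go but Table 1.

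A third is that 4.R includes everyone who starts treatment, and that the clause ends treatment, not observation. That is fair and limits the analytic damage. It leaves the shortened regimen and the missing handling rule.

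Several stronger readings are tempting, and the documents do not support them.

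- A reader might infer that every responder is stopped before the primary outcome. The and/or wording, and the interim finding that urine was often still abnormal when plasma normalised, rule that out.
- A reader might infer that both arms are hit alike. Phlebotomy normally ends earlier, on ferritin.
- A reader might infer that exclusion 3 (treatment within one month) catches every treated participant. It has an exception where pre-treatment results are available.
- A reader might infer that 4.P permits removal. Its item is "Development of a study exclusion criterion, as previously listed", and losing an inclusion criterion is not that.
- A reader might try to express the loss as months before the primary outcome. That needs a participant qualifying on plasma alone and an assumed decline curve. The plan gives no such curve and notes that hydroxychloroquine may raise porphyrins at first.

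**Conclusion.** The contradiction is real and narrow. Applied as written, the inclusion-criteria clause in 4.H cannot be followed together with the one-month-after-remission rule for any hydroxychloroquine participant who achieves all porphyrin outcomes. The minimum effect is one month of treatment per full responder on that arm, subject to the 24-month cap, with little effect on phlebotomy. The conclusion rests on reading the caption literally and on a normal urine total being no higher than 450 nmol; it needs no assumption about how fast porphyrins fall.

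The stop need not precede the primary outcome, so the exposure is to time to complete remission and to durability. How many participants would be affected is not stated; 4.R expects the smaller share of about 100 to receive hydroxychloroquine. Because the intent can be inferred from 4.C, 4.F and 4.H, most sites would probably not apply the clause this way. The practical harm is modest, but this is a stated rule that gives a wrong result if followed, and it should be corrected. Which stopping rule is clinically right is not judged here.

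**What to change.** 1. Reconcile the inclusion-criteria clause in 4.H and the Table 1 caption with 4.C, 4.F and the hydroxychloroquine end rule in 4.H. State for each Table 1 criterion whether it is entry-only or also applies during treatment. The choice of stopping rule is for the investigators and sponsor.
2. Add one line to 4.R: a fall below the entry porphyrin limits while on study is not a reason for removal or censoring, and such participants remain at risk for every treatment outcome not yet reached.

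Cost: one clarifying sentence in the protocol, a matching edit to the caption, and one line in 4.R. No new data, visits or participants are needed.

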Pretreatment plasma porphyrin levels in PCT are generally 10-25 mcg/dL (normal <0.9 mcg/dL). New skin lesions are unlikely after the plasma porphyrin concentration becomes normal. Friability, hypertrichosis, milia and areas of atrophy, scarring and hyper- or hypopigmentation improve over periods of weeks or months after this. Even scarring and the more extensive scarring and contraction (pseudoscleroderma) that sometimes occur in PCT can disappear (31), but showed little or no improvement in one series (39). Liver function abnormalities can also improve (40). Siderosis, needle-like inclusions, and red fluorescence in liver can be expected to improve or disappear, although other histological abnormalities may not (41, 42). After a remission is obtained, continued phlebotomies are usually not needed even if ferritin levels later increase to typical normal levels. However, it is advisable to follow porphyrin

levels and reinstitute treatment if porphyrin levels begin to rise. Relapses are reported to respond to another course of phlebotomies.

The time to remission with phlebotomy is not well established in the literature to serve as a standard to compare with other treatments, since many studies did not follow ferritin and plasma or urine porphyrin levels during treatment. Reports that phlebotomies for as long as one year are necessary for remission (43, 44) are not consistent with experience at most centers. Our experience and the interim analysis for this study indicate that with good adherence to scheduled phlebotomies the target ferritin can be reached in 3-4 months in most cases, and remission can be achieved in 6-7 months (19, 45).

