- 5. Normal pattern of urine porphyrins by HPLC

How quickly each of these targets and outcomes will be achieved will vary greatly among patients. Therefore, levels need to be followed closely to anticipate when visits are needed to document treatment outcomes. If less frequent visits than recommended are contemplated, site investigators should review laboratory results within 3 days of receiving the reports and determine when the next visit and the next set of tests should be done in order to document all primary and secondary outcomes.

To be considered an evaluable outcome, time to achieving each of the study outcomes listed above (e.g. time to achieving a normal plasma porphyrin level) will be documented by an abnormal finding (e.g. a high plasma porphyrin level) followed by normalization of that finding

(e.g. achieving a normal plasma porphyrin level) within a specified time interval, which is referred to as the *documentation window* for achieving that outcome. That interval/documentation window will be 4 weeks for achieving a normal plasma porphyrin concentration, and 8 weeks for achieving the later biochemical outcomes. Therefore, a single missed visit that is not within one of these windows should not lead to a missed verification of a treatment outcome.

The following study practices are recommended to document the major study outcomes:

- 1. A phlebotomy patient should return every 2 weeks after the ferritin falls to 60 ng/mL, in order to either 1) document a ferritin of 25 ng/mL on the day of the last phlebotomy, or if serum ferritin was not measured on the day of the last phlebotomy, 2) to document a ferritin level of <20 ng/mL ~2 weeks after the last phlebotomy.
- 2. Once the plasma porphyrin level drops to less than ~4 mcg/dL, this test should be repeated biweekly to ensure that, even if a visit is missed, normalization is captured within the 4-week documentation window, which will properly document time to this primary treatment outcome.
- 3. After the plasma porphyrin concentration is normal (<0.9 mcg/dL), visits should be scheduled at 4 week intervals until the other outcomes are achieved. If visits are missed intermittently, this will still allow capturing a change from abnormal to normal within an 8-week documentation window.

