centers in the U.S. The laboratory uses published methods and reports results with a clinically useful interpretation (70-72). Other laboratories can be used if equivalent results can be obtained. Although results from different laboratories are likely to be comparable, this has not been verified. Normal ranges are likely to be less comparable between laboratories than elevated abnormal values. It is desirable to use the same laboratory for porphyrin testing throughout the study. In general, Quest, LabCorp, ARUP or Mayo are suitable for urine and plasma porphyrin measurements. However plasma porphyrin fluorescence peak testing is only done at UTMB and ARUP. The treatment outcomes are based on criteria stated in this protocol rather than on normal ranges stated by different laboratories, which may vary considerably.

Molecular analyses to identify *UROD* mutations are provided by the Genetic Testing Laboratory at the Icahn School of Medicine at Mount Sinai in New York City.

4.B. Design. This is an open-label comparative study of the two standard treatments for PCT. Participants will be assigned to the treatment for which they are eligible, as determined by strict medical criteria as outlined in this protocol. Participants eligible and willing to receive either treatment will be randomized across sites; however the majority of participants are expected to be assigned a treatment based on their medical indications and preference. Based on many decades of clinical experience, both treatments are accepted as effective and safe. Therefore, comparing efficacy and safety will not be an objective of these standard of care treatments. Rather, the main objectives will be to compare time needed to achieve remission, as assessed by documented primary and secondary biochemical and clinical outcomes, and the durability (i.e. lack of disease recurrence) after each treatment. Since phlebotomy and low dose hydroxychloroquine are both considered accepted alternatives for treatment of PCT, costs will be either considered standard of care and charged to insurance or supported by the Porphyrias Consortium grant for those participants without insurance.

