The treatment outcomes for this study are documentation of times to normalization of several porphyrin laboratory measurements, which occur in sequence at different times during the Treatment Phase. Study performance will be assessed by whether or not primary study outcomes are documented within specified time windows. *Documenting the time to each outcome requires an abnormal result followed by a normal result within a specified time window.* The windows of documentation for each treatment outcome are shown in Table 5. Experience to date indicates that these outcomes are usually achieved in the order shown. All outcome measures may not be documented in all patients, but with four rather than one outcome measure it is more likely that each patient will achieve documentation of at least some of these outcomes.

| Table 5. Treatment outcomes and windows for documentation | | |
|---|------------------|--|
| Treatment Outcomes | Windows for | |
| | Documentation of | |
| | Outcomes | |
| Normal plasma porphyrin level | 4 weeks | |
| Disappearance of plasma fluorescence peak | 8 weeks | |
| at ~619 nm | | |
| Normal urine total porphyrins | 8 weeks | |
| Normal pattern of urinary porphyrins | 8 weeks | |

Time to achieving each of these treatment outcomes and the location of each of these outcome windows in time during the Treatment Phase will vary among individual participants. For this reason, regular visits should be scheduled based on these windows, and less frequent visits scheduled only after examination of the most recent laboratory results.

4.H. End of treatment. The maximum duration of treatment will be 24 months, but is expected to be shorter for most participants. Treatment by phlebotomy will end when the target ferritin value is reached (≤20 ng/mL, or ≤25 ng/mL on the day of the last phlebotomy). Therefore, it is advantageous, if possible, to obtain ferritin measurements on the days of phlebotomy. Porphyrin levels will start to decrease, but will not be normal when phlebotomies are ended. Therefore the Treatment Phase of the study extends beyond the last phlebotomy until all treatment outcomes are documented. Factors that may lengthen the duration of phlebotomy treatment include marked iron overload, some loss of venous access and difficulty adhering to treatment visits.

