- **4.J. Study duration and end of study.** The duration of the study including the Follow Up Phase is at least five years. It is possible that the study will be extended further depending on results and the availability of funding. Subjects will enter the study needing treatment, and require up to 24 months of treatment and observation to document achieving the treatment outcomes, followed by at least 3 years of follow-up. Therefore, the most frequent study visits will occur during the Treatment Phase and generally the first ~12 months of the study, which includes active treatment and the treatment outcome windows to document biochemical remission. Based on the interim analysis (45) it is anticipated that the first outcome (a normal plasma porphyrin concentration) will be reached within 6-7 months, on average. Other treatment outcomes should be achieved within ~12 months, although this is uncertain at present, since such observations were not part of the interim analysis.
- **4.K. Treatment outcomes and schedule of events.** A schedule of events in tabular form and a study flow diagram are shown below. This study compares time to reaching certain efficacy outcomes with the two treatments and documents durability of treatment in terms of absence of increases in porphyrins and recurrence of symptoms.

The primary efficacy outcome is achieving a normal plasma porphyrin concentration (<0.9 mcg/mL). Secondary efficacy outcomes include achieving (1) absence of a fluorescence peak in diluted plasma at neutral pH; (2) a normal level of total urinary porphyrins; (3) a normal pattern of individual porphyrins in urine (defined as total highly carboxylated porphyrins less than coproporphyrin); (4) times to achieving intermediate improvements in these porphyrin

measures, which will be defined during data analysis; (5) absence of new skin lesions for at least 3 months; and (6) effects of susceptibility factors such as hepatitis C, inherited UROD deficiency, etc. on achieving these treatment outcomes.

Durability of treatment (i.e. absence of recurrence) is recorded as beginning with the time that treatment achieves the treatment outcomes, and extends to the time of repeat documentation of a normal plasma porphyrin concentration, assuming there have been no interim recurrences of skin manifestations.

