| Follow Up Lab tests- Hepatic Function Panel with reflex to PT and aPTT if abnormal, HCV RNA if positive at baseline | | х | х |
| Serum Ferritin [®] (follow up needed only for phlebotomy participants) | Х | х | Х |
| Dispense HCQ or begin phlebotomies | | X | |
| HCQ twice weekly or ~biweekly phlebotomies\$ | | Х | |
| Investigator review of labs to determine next visit | | PRN | X |
| Collection of urine for research testing | Х | X | X |

[figure not shown]
#Plasma porphyrin scan at neutral pH can be done at UTMB or ARUP, urine and plasma porphyrin measurements can be done at UTMB, ARUP, Mayo, Quest or LabCorp. During treatment phase once plasma levels drop to less than ~5 mcg/dL the test should be repeated biweekly

@ Serum ferritin should be done biweekly once the level drops below 60 ng/mL, until the target of ≤20 ng/mL is reached

[%]Complete Metabolic Panel should include- sodium, potassium, chloride, carbon dioxide, blood urea nitrogen, creatinine, total protein, albumin, total bilirubin, glutamic oxaloacetic transaminase [aspartate aminotransferase], serum glutamic pyruvic transaminase [alanine aminotransferase], glucose, uric acid, calcium, and phosphorous

^{\$} For participants on HCQ the coordinator will need to complete compliance forms monthly. For participants on phlebotomy the phlebotomy visit sheet will need to completed at every phlebotomy visit

Study flow diagram:

2. Laboratory evaluations

The tests listed below are required to assess safety of treatment or detect concurrent conditions that might affect treatment indications. Examples of the latter include advanced liver disease, chronic renal disease and myelofibrosis and other bone marrow disorders. The serum pregnancy test is needed in women of child-bearing potential to exclude pregnancy, because this is a reason for exclusion at the start of the study or for stopping treatment during the study.

- a. The following will be measured by the hospital clinical laboratory.
 - i) Tests done at baseline
 - Erythrocyte glucose-6-phosphate dehydrogenase activity

- Prothrombin time
- Partial thromboplastin time
- Total protein
- Albumin
- Total bilirubin
- Aspartate aminotransferase (glutamic oxaloacetic transaminase)
- Alanine aminotransferase (glutamic pyruvic transaminase)
- Iron
- Iron binding capacity
- Transferrin percent saturation
- Ferritin

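### Section 4.K prints the primary-outcome limit in mcg/mL instead of mcg/dL, a factor of 100, so typical untreated patients already count as normal

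*Combined protocol and SAP*

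**What the plan says.** Section 4.K states: "The primary efficacy outcome is achieving a normal plasma porphyrin concentration (<0.9 mcg/mL". Every other place that puts a number on normal plasma porphyrin uses a per-decilitre unit:

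- Section 2, on phlebotomy: "Pretreatment plasma porphyrin levels in PCT are generally 10-25 mcg/dL (normal <0.9 mcg/dL".
- Section 4, recommended practices for documenting outcomes: "After the plasma porphyrin concentration is normal (<0.9 mcg/dL), visits should be scheduled at 4 week intervals".
- Table 1, criterion 5.ii.a (the synopsis gives the same limits): "plasma porphyrins [>2.7 ug/dL, or >3-fold increase (relative to ULN of 0.9 ug/dL), and a fluorescence peak at ~619 nm".

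The levels at which plasma testing becomes more frequent are also per dL. Section 4 has "Once the plasma porphyrin level drops to less than ~4 mcg/dL, this test should be repeated biweekly", and the footnote to the Schedule of Events has "During treatment phase once plasma levels drop to less than ~5 mcg/dL the test should be repeated biweekly".

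Two rules make the printed limit matter. Section 4.A says: "The treatment outcomes are based on criteria stated in this protocol rather than on normal ranges stated by different laboratories". Section 4.G says: "Documenting the time to each outcome requires an abnormal result followed by a normal result within a specified time window".

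Separately, criterion 5.ii.b in Table 1 and the synopsis gives the erythrocyte-porphyrin entry limit in two forms: below 200 ug/dL, or less than a 1.5-fold increase relative to an upper limit of normal (ULN) of 80 ug/dL.

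**The concern.** A time-to-event endpoint needs one threshold. Here the section that formally defines the primary outcome gives a value 100 times the one used elsewhere, and the usual pretreatment range lies entirely below it. Under 4.K as printed, a typical participant has no abnormal starting value and so no transition to date.

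Section 4.R says times to biochemical endpoints will be determined from the study database, and 4.K is the natural place for a programmer to look for the threshold. Falling back on the laboratory's own range is ruled out by 4.A. The durability definition in 4.K prints no unit, but it reuses the term for a normal plasma porphyrin concentration that 4.K has just defined, so it depends on the same limit.

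For the erythrocyte criterion, the question is whether the two forms describe the same entry limit.

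**Working it through.** **Primary-outcome limit.** Inputs: 0.9 mcg/mL (4.K); 0.9 mcg/dL (synopsis, Section 2, Section 4, Table 1); untreated range 10-25 mcg/dL (Section 2); plasma entry threshold 2.7 ug/dL (Table 1, synopsis); testing triggers of about 4 mcg/dL (Section 4) and about 5 mcg/dL (Schedule of Events).

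1 mL is 1/100 dL, so 0.9 mcg/mL × 100 = 90 mcg/dL, and 90 / 0.9 = 100.

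| Value (mcg/dL) | Divided by 0.9 mcg/dL | As % of 90 mcg/dL |
|---|---|---|
| 10 (low end, untreated) | 11.1 | 11.1% |
| 25 (high end, untreated) | 27.8 | 27.8% |
| 2.7 (entry threshold) | 3.0 | 3.0% |
| 4 (testing trigger, Section 4) | 4.4 | 4.4% |
| 5 (testing trigger, Schedule) | 5.6 | 5.6% |

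With 0.9 mcg/dL, every one of these values is abnormal and the outcome separates untreated from remitted patients. With 90 mcg/dL, every one is normal. A patient would need 90 / 25 = 3.6 times the top of the usual untreated range to count as abnormal at baseline.

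**Erythrocyte entry limit.** The entry criteria pair an absolute limit with a fold form four times. Two readings of a fold increase were tried: fold × ULN, and an increase added to the ULN, that is ULN + fold × ULN.

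| Criterion | Printed limit | Fold × ULN | ULN + fold × ULN |
|---|---|---|---|
| Urine, nmol | 450 | 1.5 × 300 = 450 | 300 + 450 = 750 |
| Urine, ug | 300 | 1.5 × 200 = 300 | 200 + 300 = 500 |
| Plasma, ug/dL | 2.7 | 3 × 0.9 = 2.7 | 0.9 + 2.7 = 3.6 |
| Erythrocyte, ug/dL | 200 | 1.5 × 80 = 120 | 80 + 120 = 200 |

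The first reading fits three of the four pairs and fails on the erythrocyte limit. The second fits only the erythrocyte limit. No single convention fits all four. Under the first reading, values from 120 to below 200 ug/dL meet one form and not the other.

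**The case against.** The strongest reply is that this is a unit slip that corrects itself. The outcome is worded as a normal concentration, and normal is fixed consistently elsewhere, including in Section 4's own rules for documenting this outcome. Section 4.A makes the protocol's criteria govern but does not rank 4.K above Section 4. The same endpoint was derived in the interim analysis, where 30 of 48 patients were evaluable and the median was 6 to 7 months. That result is not compatible with a working limit of 90 mcg/dL when untreated values are 10-25. If 90 were coded, almost nobody would be evaluable, and the 6-monthly DSMB review in Section 5.H, which includes the number of evaluable subjects, should expose it.

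Most of this stands. The intended unit is recoverable, and nothing indicates that the wrong one was ever used. The slip would not by itself end treatment early either: Sections 4.C and 4.H require the other porphyrin outcomes as well before hydroxychloroquine ends, and phlebotomy stops on ferritin. But the interim analysis predates this version and does not show what the current derivation uses. Detection at a later review is also no reason to leave two thresholds in the protocol.

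A misread letter in the PDF text is possible but unlikely. The sentence is clean body text, and mcg/dL is read correctly in Section 2, Section 4 and the Schedule of Events. A look at the source page settles it.

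On the erythrocyte limit, an inclusive 'or' makes the 1.5-fold form redundant, because any value below 120 is already below 200. Criterion 5.ii.b also lets the investigator accept elevations with a non-porphyric cause, and exclusion criterion 1 screens out other cutaneous porphyrias. This point is therefore a clarification only.

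**Conclusion.** The concern holds. As printed, the 4.K limit is 100 times the one used in the rest of the protocol (90 against 0.9 mcg/dL) and cannot work with the protocol's own pretreatment figures. It should be fixed because it is the decision threshold in the definition of the primary outcome. The consequence depends on whether anyone derives the endpoint from 4.K literally, which the documents do not show. They give no distribution of individual porphyrin values, so the number of participants affected cannot be calculated. The sample-size statement in Section 4.R is unaffected.

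The erythrocyte mismatch (120 against 200 ug/dL under the convention that the other three pairs follow) is real but minor. The documents do not show which figure is intended.

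**What to change.** In Section 4.K, change the unit of the primary-outcome limit from mcg/mL to mcg/dL, matching Section 4. Confirm that the database derivation of time to normal plasma porphyrin uses a limit of 0.9 mcg/dL, and that stored results, including those transferred from the period before the consortium, carry that unit.

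In Table 1 and the synopsis, reconcile criterion 5.ii.b so that its absolute and fold forms give one number, and say whether a fold increase means fold × ULN throughout.

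The cost is one unit in 4.K, one clarified line in two places and a check of the derivation. Data collection does not change.
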